7.1 DEMOGRAPHIC AND OTHER BASELINE CHARACTERISTICS

Only descriptive statistics are planned for this section of the report. All baseline analyses will be done for the cohort resulting from the 1:1 matching and for the Treated Set, respectively. The analysis sets will be stratified by treatment group to investigate demography, severity of atrial fibrillation and further baseline characteristics (incl. risk scores for stroke and bleeding measured by CHA₂DS₂-VASc and HAS-BLED).

7.2 CONCOMITANT DISEASES AND MEDICATION

Only descriptive statistics are planned for this section of the report and all analyses will be done for the cohort resulting from the 1:1 matching and for the Treated Set, respectively.

7.3 TREATMENT COMPLIANCE

Not applicable.

7.4 PRIMARY ENDPOINT(S)

The analysis of the primary endpoint will be based on the patient cohort resulting from the 1:1 matching. Time until termination of treatment will be presented for both treatment groups (Dabigatran etexilate vs. VKA) by Kaplan-Meier estimates and displayed graphically, respectively. Especially for time points 3, 6, 9 and 12 months Kaplan-Meier estimates for persistence will be calculated.

The comparison of persistence between the treatments with dabigatran etexilate versus VKA will be conducted by means of the stratified Log-rank test, which takes dependencies resulting from the matching of the treatment groups into account. Patients who discontinue

study prematurely and without documented treatment discontinuation will be censored at study termination. Patients completing the study as planned will be censored at the day after last visit, if no earlier treatment discontinuation is documented. Association between patient characteristics (incl. method of treatment) and persistence will be determined by means of cox regression (univariate and multivariate model). First, univariate regression for each of the independent variables will be performed. Afterwards, all covariates will be entered into a stepwise multivariate regression. The entry level will be $p=0.5$ and the stay level $p=0.1$. Baseline characteristics will be presented stratified by patients who discontinued the study prematurely versus no discontinuation.

A multivariate Cox Regression model (including factors for the calculation of the propensity score and the choice of treatment) will be used as sensitivity analysis. All patients, who are within the “common support” of the empiric PS density function (instead of the matched pairs), will be included in this analysis. The “common support” will be determined after patients with a propensity score above the 97.5% percentile and below the 2.5% percentile have been excluded for each treatment group, respectively. This will be done to avoid high influence of patients with extreme PS.

The following covariates will be used –depending on the sample size- for the Propensity Score Matching and the sensitivity analysis

- CHA₂DS₂-VASC Score (<2, ≥ 2)
- HAS BLED-Score (<3, ≥ 3)
- Age at registration (<65, 65-<75, ≥ 75)
- Previous stroke (Yes, No)
- Treatment (VKA, Pradaxa[®]) (sensitivity analysis only)

and the following covariates will be used –depending on the sample size- for the Cox regression

- CHA₂DS₂-VASC Score (<2, ≥ 2)
- HAS BLED-Score (<3, ≥ 3)
- Age at registration (<65, 65-<75, ≥ 75)
- Previous stroke (Yes, No)
- Medical specialty of attending physician (Internist, Cardiologist, General practitioner, Other)
- Treatment (VKA, Pradaxa[®]).

Additionally, the following subgroups will be presented for persistence (overall and for each treatment group):

- CHA₂DS₂-VASC-Score (<2, ≥ 2)
- Age (<65, 65- <75, ≥ 75)
- Previous stroke (Yes, No)
- Medical specialty of attending physician (Internist, Cardiologist, General practitioner, Other)
- Daily dose of Pradaxa[®] at initial visit (2x110mg daily, 2x150mg daily) [Patients treated with Pradaxa[®] only]
- HAS-BLED-Score (<3, ≥ 3).

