4.1.2 Allocation of patients and treatment

Each physician must include the first 4 successive eligible AF patients to whom he has decided to prescribe anticoagulant therapy with either dabigatran etexilate or VKA.

Inclusions must be alternated in a ratio of 1 patient on dabigatran etexilate to 1 patient on VKA so as to ensure equal treatment group sizes. The consecutive inclusion of the first 4 eligible AF patients is intended to prevent a selection bias in the choice of patients.

To allow comparability of the patients between the cohorts, matched pairs of dabigatran etexilate and VKA patients are formed for the analysis.

The decision to treat is made irrespective of participation in this NIS and is taken before any consideration of participation.

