5.1 Target parameters

5.1.1 Primary and secondary endpoints

Primary endpoint:

- Proportion of patients still being treated at the time of the 12-month visit with the initially allocated anticoagulant, defined as Kaplan Meier estimate at 12 months for persistence, stratified for dabigatran etexilate and VKA. Persistence is defined as the time between initiation and permanent termination of therapy ⁽²⁰⁾. The start of treatment (documented in the CRF of visit 1) is documented as the start date and the date of discontinuation of treatment with Pradaxa® or VKA as the time of permanent termination of therapy

Secondary endpoints:

- Proportion of patients with low, medium or high adherence at the time of the 6-month visit, stratified for dabigatran etexilate and VKA; categorisation is done on the basis of the Morisky questionnaire.
- Reasons for permanent treatment discontinuation.

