The analysis is performed on the basis of the patient cohorts resulting from the 1:1 matching. Kaplan Meier estimates for the time to discontinuation of treatment (cf. definition in section 5.1.) will be calculated separately for the dabigatran and the VKA patient group and illustrated graphically. In particular, the Kaplan Meier estimates for persistence at time 3, 6, 9 and 12 months will be reported. The comparison in terms of the persistence of patients on treatment with dabigatran versus VKA will be performed by means of the stratified log-rank test, which takes account of the dependency of treatment groups resulting from matching (cf. Klein, Moeschberger, 1997, ²²). Patients who discontinued the study prematurely and for whom no treatment discontinuation is documented will be censored at the time of study discontinuation. Patients who end the study as planned will be censored on the day after the last visit if no previous treatment discontinuation is documented.

The absolute number and proportion of patients discontinuing the initial treatment in the course of the study will be summarised overall and according to the reasons for discontinuation for the dabigatran and VKA cohorts.

The association of patient characteristics (including treatment allocation) with persistence will be investigated by means of Cox regression models (univariate and multivariate models). Baseline characteristics will be presented stratified for patients who discontinue the treatment in the course of the study and those who do not.

A multivariable Cox regression model (including the factors used for calculating the PS and choice of treatment) will be reported as a sensitivity analysis. For this analysis, all patients who are within the common supports of the empirical density function of the PS (instead of matched pairs) will be included; the common support is determined after excluding patients with a propensity score above the 97.5% percentile and below the 2.5% percentile in each treatment group in order to avoid a strong influence from patients with extreme PS values.

Adherence

The analysis is performed on the basis of the patient cohort resulting from 1:1 matching. The Morisky questionnaire consists of 8 questions and will be presented at the time of the 6-month visit. The analysis and categorisation of patients into the categories

- poor adherence (score >2)
- medium adherence (score=1, 2) and
- high adherence (score=0)

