the power for a descriptive p value ≤ 0.05 in a 2-tailed test for the same persistence rates is as follows (dependent on the VKA persistence rate):

Assumed VKA persistence rate*	51%	53.8%	56.5%
Power	97.8%	84.8%	61.1%

* The calculations were performed with ADDPLAN6 and are based on survival time analysis test statistics and the endpoint variables "Time to permanent treatment discontinuation".

Reasons for change 3:

After 6 months of site and patient recruitment it became evident that the targeted patient and site numbers will not be met and that recruitment time should be longer.

Therefore the planned patient number will be reduced to 1600 and site number to 800.

Observational Plan

Non-interventional study

Local Amendment

Local Amendment Number:	Local Amendment 2			
Country	Germany			
Date:	04. JAN 2016	 To be implemented only after documented approval of the IRB / IEC / Competent Authorities		
EudraCT No.:	n.a.	 To be implemented immediately in order to eliminate hazard – IRB / IEC / Competent Authority to be notified of change with request for approval		
BI Trial No.:	1160.218			
Investigational Product(s):	Pradaxa®	 Can be implemented without IRB / IEC / Competent Authority approval as changes involve logistical or administrative aspects only		
Title:	Drug persistence/adherence in patients being treated with Pradaxa® (dabigatran etexilate) or vitamin K antagonists (VKA) for stroke prevention in non-valvular atrial fibrillation (AF)			
Rationale for Local Amendment:	
After 15 months of patient recruitment 1050 / 1600 patients have been included until December 2015. For a meaningful data analysis and interpretation, the targeted patient number of 1600 patients should be met.
 
Therefore, recruitment time will be prolonged for one more year to 27 months (LPI December 2016), thus study duration will also increase. LPO is now planned for December 2017.
 
Other timelines will change accordingly.
 
In case 1600 patients will be included earlier, recruitment may be stopped before December 2016.
 
As this amendment is administrative and does not change the content or the nature of this non-interventional study, for readability reasons we refrain from changing every sentence in which site numbers, patient numbers or timelines are mentioned, except for the front page, study synopsis and statistics section.
			
Page 1 of 3				

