5. ENDPOINT(S)

5.1 PRIMARY ENDPOINT(S)

Proportion of patients, who are still treated with the initial assigned anticoagulant at 12-months visit, derived by Kaplan-Meier estimator for persistence at 12 months, stratified for dabigatran etexilate and VKA. Persistence is defined as the time in months between initiation, i.e. date of first visit, and permanently discontinuation of treatment with Pradaxa® or VKA. Patients who discontinue study prematurely and without documented treatment discontinuation will be censored at date of study termination. Patients completing the study as planned will be censored at the day after last visit, if no earlier treatment discontinuation is documented.

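### The primary endpoint is persistence at 12 months, but the arms are compared only over the whole follow-up, and no 12-month difference or confidence interval is specified

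*SAP*

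**What the plan says.** Protocol 5.1.1 makes the primary endpoint a proportion at a fixed time, "defined as Kaplan Meier estimate at 12 months for persistence", and SAP 5.1 agrees: "derived by Kaplan-Meier estimator for persistence at 12 months, stratified for dabigatran etexilate and VKA". Both sections also define persistence itself as a time, from initiation to permanent discontinuation. The primary objective (Protocol 2.2) is to compare persistence between the two drugs.

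The comparison is described in SAP 7.4: "The comparison of persistence between the treatments with dabigatran etexilate versus VKA will be conducted by means of the stratified Log-rank test". Protocol 7.3 describes the same test as one "which takes account of the dependency of treatment groups resulting from matching". Protocol 4.1.2 says that "matched pairs of dabigatran etexilate and VKA patients are formed for the analysis".

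At fixed times the plan gives per-arm estimates: "Especially for time points 3, 6, 9 and 12 months Kaplan-Meier estimates for persistence will be calculated". Both documents add univariate and multivariate Cox models that include treatment, and a Cox sensitivity analysis in patients within common propensity-score support. Neither names a between-arm difference at 12 months, its standard error, an interval or a fixed-time test. Neither mentions proportional hazards.

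The current power statement (Local Amendment 1, Change 3, replacing Protocol 7.5) refers to a "2-tailed test for the same persistence rates" but bases the calculation on survival-time test statistics. All analyses are declared descriptive and exploratory.

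**The concern.** The endpoint is one number per arm, the height of the curve at month 12. A log-rank test compares hazards over all of follow-up. Under proportional hazards, equal curves and equal 12-month persistence are the same hypothesis. Otherwise they are not: curves can separate early and meet at month 12, or cross and end apart.

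Stratifying on matched pairs sharpens this. A pair contributes only when its first observed exit is a treatment stop, and what the partner does afterwards is not used. The test therefore leans towards who stops earlier.

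What is at stake is interpretation. The report could show a small p-value beside nearly equal 12-month estimates, or a large one beside a clear gap, with no interval on the 12-month scale to help the reader. A descriptive study is mainly expected to give the size of a difference and its precision. For its own primary endpoint, this plan specifies neither.

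**Working it through.** **Inputs from the documents** (Local Amendment 1, Change 3): 1056 matched patients, so 528 pairs; 15% drop-out at one year; dabigatran persistence 63%; VKA persistence 53.8% in the middle case; two-sided 0.05; stated power 84.8%.

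**Assumptions:** exponential drop-out, no within-pair correlation, pairs as strata, follow-up to month 12 unless a patient stops or drops out.

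**1. The plan's own figure.** With constant hazards, HR = ln(0.63)/ln(0.538) = 0.745. Write a = −ln(persistence) and c = −ln(0.85) = 0.1625. The probability of an observed stop is a/(a+c) × [1 − exp(−(a+c))].
- Dabigatran: 0.4620/0.6246 × (1 − 0.5355) = 0.344
- VKA: 0.6199/0.7824 × (1 − 0.4573) = 0.430
- Events: 528 × (0.344 + 0.430) ≈ 408
- Schoenfeld: √408/2 × |ln 0.745| − 1.96 ≈ 1.01, so power 84.4%

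This reproduces 84.8% to within half a point. The stated figure is thus the power of an unstratified survival test under proportional hazards.

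**2. Precision of the 12-month difference.** The Greenwood variance per arm is S²/n × a/(a+c) × (exp(a+c) − 1).
- Dabigatran: 0.3969/528 × 0.7398 × 0.8674 = 0.000482
- VKA: 0.2894/528 × 0.7923 × 1.1867 = 0.000515
- SE = √0.000997 ≈ 0.0316; half-width 1.96 × 0.0316 ≈ 6.2 points
- Power for 9.2 points: 0.092/0.0316 − 1.96 ≈ 0.95, so about 83%

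The expected result in this case is 9.2 points, with an interval of about 3.0 to 15.4.

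**3. Pair-stratified log-rank, proportional hazards.** Summed rate 0.4620 + 0.6199 + 2 × 0.1625 = 1.407. Informative pairs: 528 × (1.0819/1.407) × (1 − exp(−1.407)) ≈ 307. The VKA patient stops first in q = 0.6199/1.0819 = 0.573 of them. Power = Φ{[(2q − 1)√307 − 1.96]/√(4q(1 − q))} ≈ 72.6%.

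**4. Non-proportional hazards.** One arm has k times its own later hazard in months 0 to 3 and the other a constant hazard (k = 1). Each arm is calibrated to its 12-month persistence S, so month-3 persistence is S^(k/(k+3)). For S = 58% this gives 0.58^(1/4) = 87% with no excess, 0.58^(1/3) = 83% at 1.5-fold and 0.58^(1/2) = 76% at 3-fold.

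Rejection rates from 2000 to 3000 simulated studies per scenario (ranges show separate runs):

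| 12-month persistence and early excess | Pair-stratified log-rank | Ordinary log-rank | 12-month difference |
|---|---|---|---|
| 58% both; 1.25-fold in one arm | 6% | 6% | 5% |
| 58% both; 1.5-fold | 8–9% | 6–7% | 4–5% |
| 58% both; 2-fold | 16% | 8% | 5% |
| 58% both; 3-fold | 34–36% | 14–15% | 5% |
| 63% vs 53.8%; none | 72–74% | 83–85% | 82–83% |
| 63% vs 53.8%; 1.5-fold, dabigatran | 54% | 77% | 83% |
| 63% vs 53.8%; 3-fold, dabigatran | 18–19% | 55–57% | 82–84% |
| 63% vs 53.8%; 2-fold, VKA | 94% | 94% | 83% |
| 63% vs 53.8%; 3-fold, VKA | 99% | 97–98% | 84% |
| 63% vs 53.8%; 3-fold, both arms | 74% | 85% | 83% |

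The log-rank results move with curve shape in both directions. The 12-month difference stays near 5% when 12-month persistence is equal and near 83% when it differs by 9.2 points.

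**The case against.** The strongest case for the plan is that the log-rank test fits the objective. Persistence is defined as a time, the objective is to compare persistence, and the power calculation uses time to permanent discontinuation. This stands: the mismatch is with the endpoint as defined, not with the objective.

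The plan also offers more than a p-value. The Cox models include treatment and would give a hazard ratio. The curves and per-arm estimates at 3, 6, 9 and 12 months would make early separation or crossing visible, and the 12-month point difference follows by subtraction. This stands too. What remains missing is the precision of that difference and any stated comparison at 12 months. Since every analysis is descriptive, no confirmatory decision depends on the test.

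A reader might go further and infer that the log-rank test is wrong here and should give way to the 12-month difference. The documents do not support that. They give no curve shapes; a mild early excess changes little (6% to 9% rejection at 1.25-fold to 1.5-fold); and when the VKA arm both stops earlier and ends lower, the log-rank is the more sensitive method. Nor is there a general power gain from targeting 12 months. Under proportional hazards the gap of about 10 points to the pair-stratified test comes from the stratification; an ordinary log-rank matches the 12-month difference. Pairs as strata is itself the natural reading, but neither document spells it out.

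**Conclusion.** The concern holds in a limited form. The primary endpoint is a 12-month proportion, every planned between-arm comparison uses the whole follow-up, and no 12-month difference or interval is specified. Where hazards are not proportional, the log-rank result and the endpoint can point different ways: about 9% to 35% rejection at equal 12-month persistence for an assumed 1.5-fold to 3-fold early excess, and power of about 18% to 99% for a true 9.2-point difference.

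The persistence rates in the power scenarios, the sample size and the drop-out are the plan's. The equal 58% level, the early-hazard shapes and the use of pairs as strata are assumptions, and the likelihood of the shapes is unknown. The figures show what can happen; they do not predict that the study will report a misleading result. The 6.2-point half-width also assumes that patients who do not drop out are followed to month 12. Completers whose last visit falls earlier would be censored before then and would widen it.

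The change is worth making because it is nearly free. The gap affects interpretation and does not invalidate the planned analysis.

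**What to change.** In SAP 7.4, add the difference in 12-month Kaplan-Meier persistence (dabigatran minus VKA) in the matched group, with a 95% confidence interval that allows for the matching, for example by bootstrap over matched pairs. Name it as the effect estimate for the primary endpoint. Report the stratified log-rank beside it, described as the test of the whole time-to-discontinuation curve, and say whether its strata are the matched pairs.

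The cost is a few SAP sentences and a little extra output, with no new data, visits or patients. The drawback is that the 12-month contrast is less sensitive than the log-rank when the arm with worse persistence also stops earlier: about 84% against 97% to 99% at a 3-fold early excess. Reporting both keeps that information.

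### The stepwise Cox model for persistence (entry 0.5, stay 0.1) does not keep treatment in, so it can drop treatment or report a hazard ratio distorted by selection

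*SAP*

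**What the plan says.** SAP 7.4 states the aim as follows: "Association between patient characteristics (incl. method of treatment) and persistence will be determined by means of cox regression (univariate and multivariate model"). Univariate models for each factor come first. Then: "Afterwards, all covariates will be entered into a stepwise multivariate regression". A factor may enter at p=0.5 and stays at p=0.1.

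The candidate list for this regression has six factors: CHA2DS2-VASc score (2 categories), HAS-BLED score (2), age (3), previous stroke (2), "Medical specialty of attending physician (Internist, Cardiologist, General practitioner, Other") and treatment. Treatment is listed like the others. Neither document says that it stays in regardless of its p-value.

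Protocol 7.3 plans the same analysis: "The association of patient characteristics (including treatment allocation) with persistence will be investigated by means of Cox regression models", univariate and multivariate. It is silent on variable selection, so the stepwise rule is the SAP's own method choice and does not conflict with the protocol.

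SAP 7.4 also plans a sensitivity analysis: "A multivariate Cox Regression model (including factors for the calculation of the propensity score and the choice of treatment"). No selection is stated for it. Its covariates are the four propensity-score factors and treatment. Physician specialty is not among them.

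**The concern.** The rule can remove the one factor that both documents name as part of this analysis. Two consequences follow.

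- **Treatment may drop out.** The stepwise model is the only planned model that holds treatment together with physician specialty. If treatment is removed, no treatment hazard ratio adjusted for specialty is reported.
- **Treatment may stay because it passed p<0.1.** Its hazard ratio is then, on average, too far from 1, and the printed interval and p-value ignore the selection. The same applies to the other five factors.

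**Working it through.** **Inputs** (Protocol 7.5 as revised by Local Amendment 1): 1056 matched patients, so 528 per group; dabigatran 12-month persistence 63%; VKA persistence 51%, 53.8% or 56.5%; 15% drop-out at one year; two-sided 0.05. Assumed here: exponential times to discontinuation and to drop-out.

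**Step 1. Hazards and events.** The discontinuation hazard is λ = −ln(persistence) and the drop-out hazard is δ = −ln(0.85) = 0.1625. Expected events per group are 528 × λ/(λ+δ) × (1 − exp(−(λ+δ))). This gives 181.4 for dabigatran and 241.0, 227.0 and 213.6 for VKA. HR = ln(0.63)/ln(VKA persistence).

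**Step 2. Reproduce the plan's power.** With z = |ln HR| × √events / 2, power = Φ(z − 1.96).

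| VKA persistence | HR | Events | z | Power, recomputed | Power, stated |
|---|---|---|---|---|---|
| 51% | 0.686 | 422 | 3.870 | 97.2% | 97.8% |
| 53.8% | 0.745 | 408 | 2.970 | 84.4% | 84.8% |
| 56.5% | 0.809 | 395 | 2.103 | 55.7% | 61.1% |

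The first two agree closely and the third does not. The stated 61.1% implies z = 0.282 + 1.960 = 2.242. Step 3 therefore gives both versions for that column.

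**Step 3. Effect of the 0.1 stay level.** P(treatment lost) = Φ(1.645 − z). Average overstatement of the log hazard ratio when kept = E[Z | Z>1.645]/z, with Z normal with mean z and variance 1.

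| VKA persistence | P(lost) | Overstatement when kept | Mean HR when kept (true HR) |
|---|---|---|---|
| 51% | 1.3% | 1% | 0.68 (0.69) |
| 53.8% | 9.3% | 6% | 0.73 (0.75) |
| 56.5% | 32.3% | 25% | 0.77 (0.81) |
| 56.5%, z from stated power | 28% | 21% | |

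**Step 4. Simulation of the stepwise rule.** Two simulations ran the full rule with 1056 patients and no covariate effects. The covariate frequencies were assumed, because the documents give none.

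- 1500 runs per scenario: treatment absent in 1.9%, 8.4% and 33.6% (Monte Carlo standard error 0.4, 0.7 and 1.2 points).
- 900 runs per scenario: treatment absent in 1.2%, 10.1% and 29.0%.
- At 56.5% in the first simulation, the mean log HR when kept was −0.267 against a true −0.212. The full model without selection gave a mean of −0.212, with 95% interval coverage of 0.953.

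**Step 5. The other factors.** If all five were null and independent, at least one would be kept with probability 1 − 0.9^5 = 41%. The simulations, with scores that overlap age and stroke, gave 39% to 42%. This is a worst case, since some of these factors are expected to matter.

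**Step 6. Is selection needed?** Parameters: 1 + 1 + 2 + 1 + 3 + 1 = 9. Events per parameter: 395/9 = 44 to 422/9 = 47.

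**Step 7. Shortfall scenario.** Local Amendment 2 reports: "After 15 months of patient recruitment 1050 / 1600 patients have been included until December 2015". The target is still 1600, so this is a lower bound and not the plan. With 525 per group and 66% matched, 346.5 per group remain, with 277, 268 and 259 events. P(lost) becomes 7%, 22% and 48%, and events per parameter 29 to 31.

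**The case against.** The strongest case against is about weight. Protocol 7 and SAP 7 call every analysis descriptive, and no endpoint rests on this model. Treatment is reported by the Kaplan-Meier curves, the stratified log-rank test, the univariate model and the sensitivity model. Four of the five other factors are already matched on. All of this stands and limits the severity.

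The specialty argument is also weaker than it first looks. SAP 7.4 plans persistence by specialty within each treatment group. Protocol 4.1.2 has each physician alternate dabigatran and VKA patients, which should largely balance specialty at enrolment. Even so, neither supplies a specialty-adjusted treatment hazard ratio. Matching is not stated to be within site, so balance after matching is not assured.

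On size, the effect is small at 51% and modest at 53.8%. It is material only at the smallest assumed difference, and there the plan's own power figure gives about 28% loss in place of 32%. That changes the number and not the conclusion.

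Finally, pruning overlapping predictors is a defensible exploratory aim, and an entry level of 0.5 is lenient. But the stay level of 0.1 decides what is reported, and descriptive status does not make selected estimates or their intervals accurate.

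**Conclusion.** The concern holds. As written, the six-factor association model can lose treatment, and what it keeps is filtered by p<0.1. Over the plan's own range of VKA persistence, treatment is lost in about 1% to 32% of analyses, and its log hazard ratio is overstated by about 1% to 25% when kept. These figures rest on exponential times, 528 matched patients per group and 15% drop-out. The simulations also rest on assumed covariate frequencies and null covariate effects. The primary comparison and the sensitivity Cox model are not affected. The change is worth making as an improvement to an exploratory analysis.

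**What to change.** In SAP 7.4, delete the stepwise sentence and the entry and stay levels. Fit one prespecified Cox model with all six listed factors, treatment always included. Report every hazard ratio with its 95% confidence interval beside the univariate result. The SAP makes the covariate list depend on sample size; if a shorter list is needed, fix it in advance and not by p-value. At minimum, state that treatment is retained and label any remaining selection as exploratory.

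This needs less programming than now planned. The one downside is that both scores contain age and stroke, so their mutually adjusted hazard ratios need cautious reading. With assumed covariate frequencies, the standard errors of the two scores, age and stroke rise by about 7% to 11% over the univariate models, and that of treatment by 1% or less.
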